## Analysis Notes

Analyses of the primary outcome will be limited to the first in-person appointment for each patient enrolled in the study. We will run a sensitivity analysis that includes patients who only attend telehealth appointments during the study.

Recent work suggests that OLS regressions are appropriate in randomized experiments with binary outcome variables such as ours (Gomila, 2021).

As the treatment variation is at the individual level, we will report heteroskedasticity-robust standard errors. We will also explore the impact of clustering these standard errors at the clinic and clinic-date levels to allow for dependence across observations within these clusters. We will also investigate heterogeneity across clinics that vary along characteristics of interest, including prior-year vaccination rates.

We may run additional robustness checks. These checks may include focusing on additional inclusion/exclusion criteria (e.g., including subsequent visits with alerts for a given patient) and subpopulations (e.g., different visit types).

## Other Pre-specified Outcomes

Other Pre-specified Outcomes listed below include flu outcomes (diagnosis, complications) and COVID-19 vaccination. If there are any differences in these outcomes as a function of study

arm, the mechanism would almost certainly be increased flu vaccination. Therefore, we will only run analyses on Other Pre-specified Outcomes for analyses above where there is a significant difference in flu vaccination.

1. High confidence flu diagnosis

Patient received a flu diagnosis via a positive polymerase chain reaction [PCR]/antigen/molecular test (yes/no) during the 2022-23 flu season (from the patient's appointment date through April 30, 2023)

[Time Frame: Up to 8 months]

2. "Likely flu" diagnosis

Received a "high confidence flu" diagnosis (with positive polymerase chain reaction [PCR]/antigen/molecular test) and/or "likely flu" diagnosis (as assessed via International Classification of Disease [ICD] codes or Tamiflu administration or positive PCR/antigen/molecular test) (yes/no) during the 2022-23 flu season (from the patient's appointment date through April 30, 2023)

Note that "likely flu" is a superset of the "high confidence flu" diagnoses.

[Time Frame: Up to 8 months]

3. Flu complications

Diagnosed with flu-related complications (yes/no) during the 2022-23 flu season (from the patient's appointment date through April 30, 2023)

[Time Frame: Up to 8 months]

4. ER visits

Number of ER visits from the patient's message appointment date through July 31, 2023

[Time Frame: Up to 11 months]

5. Hospitalizations

Number of hospitalizations from the patient's message appointment date through July 31, 2023

[Time Frame: Up to 11 months]

6. COVID-19 vaccination rates

Received at least one COVID-19 vaccination (yes/no) during the 2022-23 flu season (from the patient's appointment date through April 30, 2023)

[Time Frame: Up to 8 months]

7. Flu vaccination during the 2022-2023 season

Patient receives a flu vaccine (yes/no) during the 2022-23 flu season (from the patient's appointment date through April 30, 2023)

[Time Frame: Up to 8 months]

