While most recover from influenza without treatment, the elderly, those with comorbidities, and other high-risk individuals can experience complications such as pneumonia, other respiratory illness, and death (Rothberg et al., 2008; Turner et al., 2003; WHO, 2010). Geisinger, a large health system in Pennsylvania, has partnered with Medial EarlySign (Medial; www.earlysign.com) to develop a machine learning (ML) algorithm to identify patients at risk for serious (moderate to severe) flu-associated complications based on existing EHR data. As part of our recent Roybal-funded pilots, Geisinger deployed this system during the 2020–21 and 2021–22 flu seasons and sent patients in the top 10% of predicted risk special messages (in addition to standard health system efforts) encouraging vaccination. Interim data from both pilots reveal that notifying patients about their high-risk status increases vaccination, but vaccination is not further increased by informing patients of how their risk was determined (Shermohammed et al., 2021) or by informing them of contributing risk factors from their medical records (Rosenbaum et al., 2021). Compared with patients, clinicians may be more receptive to information about individual patient risk factors, given their better understanding of medical diagnoses contributing to flu risk.

The present study will test the effectiveness of a clinician-facing nudge (e.g., salient, risk-based alert vs. a standard alert) on flu vaccination. This study builds on previous work supporting the effectiveness of salient alerts in encouraging flu vaccination (Kim et al., 2018; Patel et al., 2017) and extends it by focusing on alerts for people at high risk for flu and flu complications.

Specific Aims

Evaluate via randomized controlled trial the efficacy of a clinician-facing, EHR alert-based nudge promoting flu shots, alerting clinicians to their patients' high-risk status (with or without personalized contributing factors).

PROCEDURES

Research Design

Patients from the high-risk sample (primary target population) will be randomly assigned to one of at least two study arms. If necessary, we will randomize at the clinician or clinic level. Outcomes during the 2022–2023 flu season will be compared between study arms.

Study Population

1) Patients

Inclusion Criteria:

- Age 18+
- Have been determined to be in the top 20% of risk through Medial's ML algorithm

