- Attend an appointment where the flu alert fires (Geisinger sets when flu alerts start and ends--between ~9/1/2022 and ~4/30/2023, as well as the trigger conditions for the alert, which includes valid departments and visits and excludes contraindications like Guillain-Barre syndrome)

2) Clinicians

Inclusion Criteria:

- Any Geisinger clinician who sees patient-participants in our study for an appointment where their flu shot alert fires

Recruitment and Enrollment

All patients will be recruited and enrolled from Geisinger; Massachusetts Institute of Technology (MIT)/National Bureau of Economic Research (NBER) collaborators will not be involved in recruitment or enrollment. Patients meeting the primary target population criteria will be enrolled into one of the experimental conditions. Anticipated enrollment number for this primary target population is 90,000. Only Geisinger clinicians for this primary target population will see the salient, risk-based alert for patients who were randomized to trigger it. Clinicians of patients who are not part of the study population will still see the standard flu alert if their patients are eligible for it as part of Geisinger's standard of care.

Detailed Study Procedures

Patients in the top 20% of risk for flu and flu complications based on the Medial EarlySign flu algomarker will be randomized to trigger a standard flu alert (specifically, a best practice alert) or a salient, specialized alert for clinicians throughout the 2022–23 flu season, stating the patients' level of risk (e.g., top 3%, top 10%, or top 20%). Among those who triggered the high-risk alert, we may further randomize this group to be shown or not shown the top factors contributing to patients' risk, based on Medial's algorithm. The high-risk alert will also include

text and color features to make the alert stand out among other alerts. Additionally, the high-risk alerts will be given priority, such that they are displayed above other unprioritized alerts (they will still show below high-priority alerts). The precise language and look of the alerts may change slightly from the attached drafts, as we are working with multiple teams at Geisinger, but the drafts are representative of the types of alerts that will be shown.

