Geisinger introduces flu-related alerts on September 1st. As part of the research planning, randomization will occur in June 2022, in order to provide enough time to import risk scores and high-risk factors into Epic, so these data can be used to trigger the proper alerts. Because this intervention is timed to the 2022–23 flu season, the intervention period will begin ~9/1/22.

The primary outcome will be flu vaccination at the scheduled appointment, as recorded in the Geisinger EHR. We may limit the timeframe of the primary outcome to end earlier in the flu season (e.g., December), based on data suggesting that most patients get their flu shot by the end of the calendar year. If we choose this timeframe, we will still examine all data collected throughout the flu season. Additional outcomes to be measured between the patient's appointment and the end of the flu season will include: rates of flu diagnoses (both using the most rigorous biological tests, "high confidence flu", and using broader criteria that also include diagnosis codes and treatment information, "likely flu"), flu complications, and rates of other relevant healthcare utilization outcomes such as ER visits and hospitalizations. Finally, we will measure rates of COVID-19 vaccination in targeted patients.

Data Sources

All patients in this study will be in the top 20% of risk according to scores given by the Medial EarlySign flu algomarker. The development of this algorithm was already approved through a separate Geisinger IRB application (IRB number 2020-0211). Additionally, Geisinger deployed this system in a field study during the 2020–21 (IRB number 2020-0290) and 2021–22 flu seasons (IRB number 2021-0483) and contacted the identified patients with special messages (in addition to standard interventions conducted by the health system every flu season) to encourage vaccination.

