## Power Analysis

We expect at least 60,000 patients to be enrolled (at least 20,000 per arm). With this sample size, we will have 80% power to detect an increase in flu vaccination rates from 35% to 36.34% with two-tailed alpha = .05 for any comparison between arms.

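### COVID-19 vaccination is analysed only if flu vaccination differs significantly, but the reason given for that condition does not fit this outcome

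*SAP*

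**What the plan says.** The SAP section Other Pre-specified Outcomes lists seven outcomes under one rule and gives its reason: if these outcomes differ by study "arm, the mechanism would almost certainly be increased flu vaccination. Therefore, we will only run analyses on Other Pre-specified Outcomes for analyses above where" flu vaccination differs significantly. Item 6 falls under the rule: "Received at least one COVID-19 vaccination (yes/no) during the 2022-23 flu season", counted from the appointment date through April 30, 2023.

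The other six items are two definitions of flu diagnosis, flu complications, ER visits, hospitalizations and season-long flu vaccination. None measures a preventive service other than the flu shot. Neither Analysis Notes nor Additional Exploratory Analyses tests COVID-19 vaccination outside the rule.

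The protocol (Detailed Study Procedures) says that "the high-risk alerts will be given priority, such that they are displayed above other unprioritized alerts", while still appearing below high-priority alerts. SAP Methods adds larger headers, bold face, red font and a statement that the patient is at high risk. On the outcome itself, Detailed Study Procedures says: "Finally, we will measure rates of COVID-19 vaccination in targeted patients". Data Sources includes COVID-19 vaccination status in the outcome extract.

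**The concern.** For flu diagnosis and flu complications it is reasonable to suppose that the alert acts through the flu shot. COVID-19 vaccination is a different decision, made by the same clinician and patient, possibly at the same visit. Three features separate the high-risk arms from the Standard Alert arm, and each could act on that decision directly:

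- display priority, which may draw attention away from other prompts;
- visual salience, which may do the same;
- the high-risk label, which may itself prompt a COVID-19 shot.

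The first two would lower COVID-19 vaccination and the third would raise it. None needs flu vaccination to change. A condition based on the flu result is therefore a poor guide to whether item 6 is worth examining. If the flu result is null, the report would carry no planned estimate of the alert's effect on the one listed outcome that measures another preventive service.

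**Working it through.** **Inputs.** SAP Power Analysis gives at least 20,000 patients per arm, 35% against 36.34%, 80% power and "two-tailed alpha = .05 for any comparison between arms". Analysis 1 combines the two high-risk arms, so it compares about 40,000 with 20,000. The documents give no base rate for COVID-19 vaccination; 5% to 30% is assumed.

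**The plan's own figure.** With 20,000 per arm, SE = √[(0.35×0.65 + 0.3634×0.6366)/20,000] = 0.00479. Then 0.0134/0.00479 = 2.80, and Φ(2.80 − 1.96) = about 79.9%. The stated 80% reproduces.

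**How often the condition fails for Analysis 1.** For a true flu effect d,

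SE(d) = √[0.35×0.65/20,000 + (0.35+d)(0.65−d)/40,000], which is about 0.413 points at d = 0.

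P(significant) = Φ(d/SE − 1.96) + Φ(−d/SE − 1.96).

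| True flu effect (points) | Analysis 1 significant | Item 6 not analysed against Standard Alert |
|---|---|---|
| 0 | 5% | 95% |
| +0.5 | 23% | 77% |
| +1.0 | 68% | 32% |
| +1.34 | 90% | 10% |

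The two outcomes are about equally likely at an effect of 1.96 × 0.413 = 0.81 points.

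Analysis 2 can also meet the condition, but only for its own contrast. It compares the two high-risk arms, and the protocol gives priority to high-risk alerts generally, so it says nothing about priority.

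**What an unconditional comparison could detect.** The difference in item 6 detectable with 80% power is about 2.80 × √[p(1−p)(1/40,000 + 1/20,000)], where the square root of the bracketed sample-size term is 0.00866. The last two columns use the arm-specific variances for a drop from p.

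| Assumed base rate p | Detectable difference (points) | Power, 1-point drop | Power, 0.5-point drop |
|---|---|---|---|
| 5% | 0.53 | >99% | 78% |
| 10% | 0.73 | 98% | 50% |
| 20% | 0.97 | 83% | 31% |
| 30% | 1.11 | 72% | 24% |

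**Effect of the window.** Item 6 counts any COVID-19 shot from the appointment through April 30, 2023, up to 8 months. A shot missed at the visit and given later still counts as yes. As an illustration only, if half of a 1-point visit-level drop were made up later, 0.5 points would remain and the last column would apply.

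**The case against.** The strongest reply is that displacement is not documented. The protocol describes an order of display. No passage says that a COVID-19 alert existed or where it ranked, or that item 6 serves as a safety measure. The control arm also receives a flu alert, so only order, salience and risk content differ. This stands, and it limits the point to a plausible inference. The upward route, through the high-risk label, does not need a competing alert.

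The season-long window makes item 6 a blunt measure of what happened at the visit. This also stands. A null result on item 6 would not exclude short-lived displacement.

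A reader might infer more than the documents support in four ways:

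- *That any harm from an ineffective alert would never be examined.* With no flu effect the condition is still met by chance 5% of the time, and a significant fall in flu vaccination would also meet it. The data are extracted regardless, and the protocol plans to share a deidentified dataset. What is missing is a planned analysis.
- *That item 6 would usually go untested.* This holds only for true flu effects below about 0.8 points. At the 1.34 points used for sizing, it would be tested about 90% of the time.
- *That the SAP contradicts the protocol.* The protocol promises to measure COVID-19 vaccination. Research Design says in general terms that outcomes during the 2022–2023 "flu season will be compared between study arms". Neither promises an unconditional test of this outcome, and the SAP is the more specific rule.
- *That a COVID-19 difference would be formally attributed to flu vaccination.* No mediation analysis is planned. The sentence is only a rationale for the condition.

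**Conclusion.** The point holds as a low-cost improvement. The stated reason for the condition does not fit COVID-19 vaccination, and nothing else in the SAP analyses it. The chance that the comparison with Standard Alert is skipped ranges from about 95% with no true flu effect to about 10% at +1.34 points. The patients already planned could detect about 0.5 to 1.1 points on item 6.

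These figures assume 40,000 against 20,000 independent patients, a 35% flu vaccination rate in the Standard Alert arm and COVID-19 base rates that the documents do not give. Enrolment above the SAP's minimum would lower the skipped share for a true positive effect but leave the 95% at zero unchanged. The confirmatory analysis is unaffected. The documents do not support a claim that the alert displaces other care, only that the plan may not look.

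**What to change.** In Other Pre-specified Outcomes, exempt item 6 from the condition. Suggested wording: *COVID-19 vaccination will be compared between the two high-risk arms combined and the Standard Alert arm, two-sided with a 95% confidence interval, regardless of the flu vaccination result. This analysis is exploratory.* Add that the rationale about flu vaccination as the mechanism does not apply to COVID-19 vaccination, and note that the window to April 30, 2023 would dilute any effect confined to the visit.

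Analysis 2 need not be exempted as a displacement check, because both of its arms receive the prioritised alert.

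The cost is a short SAP edit and one regression on data already being extracted, with no added patients. The downside is one more exploratory test, to be labelled as such.

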GENERAL INFORMATION

Alerts with Risk Information to Increase Influenza Vaccinations

[name].
[contact]

March 13, 2023

IRB#: 2022-0502

BACKGROUND AND OBJECTIVES

On average, 8% of the US population gets sick from the flu each flu season (Tokars et al. 2018). Since 2010, the annual disease burden of influenza has included 9-45 million illnesses, 140,000-810,000 hospitalizations, and 12,000-61,000 deaths (CDC 2020). The CDC recommends a flu vaccination to everyone aged 6+ months, with rare exception; almost anyone can benefit from the vaccine, which can reduce illnesses, missed work, hospitalizations, and death (CDC 2019). Flu vaccination is especially important during the COVID-19 pandemic, to minimize flu/COVID-19 coinfections and conserve healthcare resources.

One barrier to vaccination is a lack of “cues to action,” and, in particular, the lack of direct recommendation from medical personnel (Schmid et al. 2017); this barrier is arguably the most effectively overcome by a simple nudge of clinicians, compared with barriers such as negative attitudes toward vaccination, low perceived utility of vaccination, and less experience with having received the vaccine. Nudges that increase clinician actions to recommend and order flu shots for their patients may therefore increase vaccinations more than attempts to nudge patients directly (e.g., by sending them text messages). Interruptive or “hard stop” alerts can help promote behavior that improves patient outcomes (Powers et al., 2018). And mechanisms that make an alert more salient can increase attention to a nudge and thus encourage action (Patel et al., 2017; Kim et al. 2017). These nudges are likely to be most effective when timely, for instance, as alerts to clinicians during those appointments (Milkman et al. 2021). In the 2020–21 flu season, Geisinger implemented a standard electronic health record (EHR) alert notifying clinicians when any outpatient they are seeing is eligible for a flu shot; yet, despite this alert, only a minority of patients are presently being vaccinated, especially at specialty appointments.

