## Scientific Background and Objectives

The CDC (Centers for Disease Control) recommends a flu vaccination to everyone aged 6+ months, with rare exception; almost anyone can benefit from the vaccine, which can reduce illnesses, missed work, hospitalizations, and death. One barrier to vaccination is a lack of "cues to action," and, in particular, the lack of direct recommendation from medical personnel; this barrier is arguably most effectively overcome by a simple nudge of clinicians, compared with barriers such as negative attitudes toward vaccination, low perceived utility of vaccination, and less experience with having received the vaccine.

Geisinger partnered with Medial EarlySign (Medial) to develop a machine learning (ML) algorithm to help identify people at risk for serious flu-associated complications based on existing electronic health record data. Eligible at-risk patients were randomized to an active control group (clinician is shown a standard flu alert) or one of two experimental groups (clinician is shown an alert indicating patient's high risk, with or without describing the patient's factors contributing to that risk).

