## Planned Analyses

**Primary Outcome:** Patient received a flu vaccine (yes/no) [Time Frame: At the 1 day visit]

**Question 1:** Do salient alerts indicating that patients are at high risk for flu and flu-related complications increase the likelihood that the patients will get vaccinated?

**Analysis 1 (Confirmatory):** We will test the hypothesis that patients whose clinicians were shown alerts with information about their risk status (patients randomized to the High-risk Alert or High-risk Alert with Risk Factors arms) will exhibit improved flu vaccination rates compared with patients in the Standard Alert arm.

For this analysis, we will run an OLS regression, including a binary predictor variable coding separately for baseline and the two High-risk Alert arms.

**Question 2:** Do alerts with information about a patient's factors that contribute to their high risk of flu and flu-related complications increase the likelihood that the patients will get vaccinated?

**Analysis 2 (Exploratory):** We hypothesize that patients whose providers were shown alerts with the factors that contributed to a patient's high risk (High-risk Alert with Risk Factors arm) will exhibit improved flu vaccination rates compared with patients in the arm with no risk factors (High-risk Alert arm).

For this analysis, we will run an OLS regression, including a binary predictor variable coding separately for each of the two High-risk Alert arms.

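### The SAP presumes that downstream differences come from vaccination, but at the difference the trial is sized to detect, a significant flu-diagnosis difference is too large for that, and error among items 1-5 is uncontrolled once vaccination differs

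*SAP*

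**What the plan says.** The SAP section Other Pre-specified Outcomes lists seven outcomes:

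- items 1 and 2: high-confidence and likely flu diagnosis
- item 3: flu complications
- items 4 and 5: ER visits and hospitalizations
- item 6: COVID-19 vaccination
- item 7: season-long flu vaccination

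It states that if arms differ on these, "the mechanism would almost certainly be increased flu vaccination". From this it derives a gate: "we will only run analyses on Other Pre-specified Outcomes for analyses above where there is a significant difference in flu vaccination". It gives no significance level, multiplicity rule, expected rate or power for these outcomes.

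The analyses that can open the gate are in Planned Analyses. Analysis 1 (confirmatory) compares "patients randomized to the High-risk Alert or High-risk Alert with Risk Factors arms" with the Standard Alert arm. Analysis 2 (exploratory) compares the two high-risk arms with each other.

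The SAP's Power Analysis concerns vaccination only. It expects at least 60,000 patients, at least 20,000 per arm, and says "we will have 80% power to detect an increase in flu vaccination rates from 35% to 36.34% with two-tailed alpha = .05". The Protocol (Recruitment and Enrollment) has a larger figure: "Anticipated enrollment number for this primary target population is 90,000". The only flu incidence in either document is in the Protocol's Background and Objectives: "On average, 8% of the US population gets sick from the flu each flu season".

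**The concern.** The sentence settles the cause of a downstream difference before any data are seen. It is safe only if vaccination is able to produce a difference of the size that would be declared significant. A rise of one or two points in vaccination changes flu incidence by a small fraction of a point, and that is well inside the sampling error of this trial.

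Other routes to a difference exist. The high-risk alert tells the clinician that the patient is at high risk of flu and its complications (SAP, Methods), and item 2 counts ICD codes and Tamiflu administration as well as positive tests. A clinician who has seen the alert could test, code or treat differently with no change in vaccination.

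What is at stake is the reading of secondary results. After a positive primary result, up to five clinical outcomes are examined per contrast with no control among them. A chance finding, or one produced by altered detection, would come with its explanation already written. The primary analysis is not affected.

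**Working it through.** **Inputs**

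- Vaccination 35% vs 36.34%, 20,000 per arm, two-sided alpha 0.05 (SAP, Power Analysis).
- Analysis 1 pools two arms: 40,000 vs 20,000.
- Control-arm flu risk 8% (Protocol, Background and Objectives). This is a US population average, used here as an assumption and varied below.
- Vaccine effectiveness (VE): no figure in the documents. Assumed 40%, with 100% as the ceiling.

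**1. The plan's own figure.** SE = sqrt(0.35×0.65/20,000 + 0.3634×0.6366/20,000) = 0.479 points. z = 1.34/0.479 = 2.80. Power = Φ(2.80 − 1.96) = 79.9%. The stated 80% is reproduced.

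**2. Smallest significant flu difference, Analysis 1.** SE = sqrt(0.08×0.92×(1/40,000 + 1/20,000)) = 0.235 points. Limit = 1.96×SE = 0.460 points.

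**3. What that implies per extra vaccination.** 0.460/1.34 = 34.4 points less flu per extra vaccinated patient.

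**4. The ceiling.** With 35% of the control arm vaccinated, a perfect vaccine puts all the flu in the other 65%. Their risk is then 8%/0.65 = 12.3%. An extra vaccination cannot on average prevent more than this, if the extra patients have the average risk of the unvaccinated. The 34.4 is 2.8 times the ceiling.

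**5. Power for flu diagnosis.** Risk in the unvaccinated is u = 0.08/(1 − 0.35×VE). The expected difference is d = u×VE×1.34 points, and z = d/SE. Power = Φ(z − 1.96) + Φ(−z − 1.96).

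- VE 40%: u = 9.30%, d = 0.050 points, z = 0.21, power 5.5%.
- VE 100%: u = 12.3%, d = 0.165 points, z = 0.70, power 10.8%.

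**6. Sensitivity.** Same formulas. The 90,000 is split 60,000 vs 30,000, assuming equal arms.

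| Control flu risk | Patients | Limit (points) | Limit/1.34 | Ceiling | Power, VE 40% | Power, VE 100% |
|---|---|---|---|---|---|---|
| 8% | 60,000 | 0.460 | 34.4 | 12.3 | 5.5% | 10.8% |
| 8% | 90,000 | 0.376 | 28.1 | 12.3 | 5.8% | 13.9% |
| 16% | 60,000 | 0.622 | 46.4 | 24.6 | 6.1% | 18.1% |
| 20% | 60,000 | 0.679 | 50.7 | 30.8 | 6.5% | 22.2% |

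The implied effect exceeds the ceiling in every row. The 35% may understate season-long vaccination in the control arm, which would raise the ceiling. At 8% risk it would reach 34.4 only if 1 − 0.08/0.344 = 77% of controls were vaccinated.

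**7. Vaccination rise at which the expected flu difference equals the limit (8% risk, 60,000).** 0.460/(u×VE): at VE 100%, 0.460/0.123 = 3.7 points; at VE 40%, 0.460/(0.0930×0.40) = 12.4 points. Power there is about 50%. For 80% power the rise must be about 5.3 or 17.5 points.

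**8. False positives among items 1-5 once the gate is open.** If independent, 1 − 0.95^5 = 22.6%. At a common correlation of 0.5, simulation gives about 18%. Stronger correlation lowers it further, and item 1 is nested in item 2.

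**The case against.** The strongest defence has four parts.

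**The 1.34 points is a detectable difference, neither a forecast nor a maximum.** This stands. A reader might infer that vaccination cannot move flu outcomes to significance in this trial; the documents do not support that. With a 5-point rise, 8% risk, VE 100% and 60,000 patients, d = 0.615 points, SE = 0.232, z = 2.65 and power is about 75%. The 60,000 is also a minimum, and patients in the top 20% of predicted risk may have more flu than the national average. The conclusion is therefore conditional on the size of the vaccination effect.

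**The gate does control error.** This stands in part. If vaccination does not differ, downstream testing on a contrast is reached only about 5% of the time, so it would be wrong to say that the plan has no error control. But the gate does nothing among items 1-5 when vaccination truly differs, which is the case the trial hopes for.

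**The sentence is hedged and serves to restrict testing; it does not instruct anyone how to interpret results.** This is fair as to its purpose. Nor are these outcomes called confirmatory, and Analysis 2, which could open the gate a second time, is labelled exploratory. A reader might infer that the SAP has committed itself to reporting any significant result as a vaccination benefit; it has not said so. Still, it is the only statement in the SAP on how such differences arise, and it presumes the answer.

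**The arithmetic covers flu diagnosis only.** This stands. The documents give no rates for complications, ER visits or hospitalizations, so the power result should not be extended to them.

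**Conclusion.** The point holds in conditional form. If the alert raises vaccination by about the 1.34 points the trial is sized to detect, and control flu risk is about 8%, a significant flu-diagnosis difference would have to be roughly three times what a perfect vaccine could produce. Such an estimate would owe most of its size to chance or another pathway, even if vaccination contributed a little. The ceiling is still exceeded at 20% flu risk with 60,000 patients, and at 8% risk with 90,000. It is no longer exceeded if the vaccination rise is above about 3.7 points with a perfect vaccine; at 40% effectiveness the expected difference reaches the limit only at about 12.4 points.

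Separately, once vaccination truly differs, the chance of at least one false positive among items 1-5 is about 18-23% per contrast, for correlations between 0.5 and zero. For complications, ER visits and hospitalizations, only this multiplicity point and the presumed attribution apply.

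The result rests on the general-population 8%, on assumed vaccine effectiveness, and on extra vaccinated patients having the average risk of the unvaccinated. It justifies a change to the SAP's wording and reporting and does not touch the primary analysis.

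**What to change.** In the SAP section Other Pre-specified Outcomes:

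1. Replace the attribution sentence with one that does not presume the mechanism. State that a difference too large for the observed vaccination difference to produce will not be attributed to vaccination. Define the limit as: observed season-long vaccination difference × control-arm risk / (1 − control-arm vaccination rate). For the counts in items 4 and 5, use the control-arm mean in place of the risk.
2. Report items 1-5 as estimates with 95% confidence intervals, beside the season-long vaccination difference (item 7, already collected). Give the ratio of the two only as a plausibility check. It should not be presented as an instrumental-variable estimate, because that would assume the vaccination-only pathway that is in question.
3. Label items 1-5 exploratory. If significance is to be claimed for any of them, apply Holm across the five within each contrast.

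No new data are needed: the cost is SAP wording and a few lines of code. The downside is somewhat weaker claims; for flu diagnosis, power through vaccination is in any case near alpha at the detectable difference.
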